For all continuous outcomes, such as anxiety, the basic model, to which we can add our controls and predictors. The level 1 submodel estimates how each participant's anxiety changes over the four data collection periods. The level 2 submodel will relate the inter-individual differences to intervention group and other time-invariant predictors and controls, such as medication (i.e., antidepressants) and have begun therapy (i.e., in usual care for mental health diagnoses), and will estimate a participant's initial anxiety level and rate of change in anxiety. Anxiety will be modeled in terms of random subject effects (intercept and time trends) to account for individual differences in how participants change over time. We will begin with a linear model for time but will investigate nonlinear effects as suggested by the data. Subsequent models will contain time-varying covariates (i.e., dose of intervention, weight, exercise) and thus will focus on within-participants effects, that is, whether within-participant differences in the covariates are associated with within-participant differences in anxiety. We will examine the potential of cognitive beliefs and perceived difficulty in leading a healthy lifestyle in mediating the effects of the COPE-P program on healthy lifestyle behaviors and psychological symptoms. Rather than detecting mediated effects with the causal steps approach of Baron and Kenny, we will use the Joint Significance Test established by MacKinnon, which assesses the statistical significance of the X to M relation,  $\alpha$  path, and then the M to Y relation,  $\beta$  path. If both are statistically significant, there is evidence of mediation. Models with more than one mediator are simply extensions of the single-mediator case. In our multilevel models, we will investigate mediation effects within the different levels of analysis and across levels. Finally, we will explore characteristics that may moderate healthy lifestyle behaviors, psychosocial health, and birth outcomes (e.g., race/ethnicity, age, parity, language spoken, level of education, income, marital status) in the above models. The proposed examination of mediators and moderators should allow for increased understanding of mechanisms underlying any intervention effect and different responses among the participants. The most appropriate covariance structure for the residuals  $\epsilon_{ij}$  will be determined after data collection and the correlation of responses over time is estimated. Several covariance structures will be examined and the resulting models compared for fit using the quasi-likelihood independence model information criterion (QIC) fit using SAS 9.4 (Proc MIXED).

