
Should any of the outcomes need to be dichotomized (i.e., present vs. absent), we will fit a multi-level random effects logistic regression models with time-varying covariates. The basic model, to which we will add our controls and predictors, can be written: where  $i$  indexes participants,  $t$  indexes time, COPE-P is an indicator of the intervention group, COPE-P x Time is the intervention by time interaction,  $X_k$  is a set of time-varying covariates measured for each participant  $i$  at time  $t$  and  $u_i$  is participant-specific error term. The interaction term COPE-P x Time is the test of the effectiveness of the COPE-P program. If successful, the regression coefficient will be negative, indicating that the modeled probability of psychological symptoms declined more

07/30/2021

rapidly with time in the COPE-P group than they did in the PregnancyPlus group. We will fit these models using SAS 9.4 (Proc NLMIXED).

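### The growth model for the continuous outcomes leaves the T0 arm difference free and plans no T0 adjustment, so the baseline score is used inefficiently

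*Combined protocol and SAP*

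**What the plan says.** The paragraph on continuous outcomes in the Analysis plan covers every occasion: "The level 1 submodel estimates how each participant's anxiety changes over the four data collection periods". At the second level, "The level 2 submodel will relate the inter-individual differences to intervention group and other time-invariant predictors and controls". The examples of controls are antidepressant medication and having begun therapy. The same sentence says that this submodel "will estimate a participant's initial anxiety level and rate of change in anxiety". On the form of time: "We will begin with a linear model for time but will investigate nonlinear effects as suggested by the data".

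The paragraph on dichotomized outcomes lists both an arm term and an interaction: "COPE-P is an indicator of the intervention group, COPE-P x Time is the intervention by time interaction". It adds: "The interaction term COPE-P x Time is the test of the effectiveness of the COPE-P program". That logistic model is used only if an outcome has to be dichotomized.

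Two other places bear on this. Under Hypothesis-driven analyses, the sentence that names the four primary outcomes lists t-tests, ANCOVA and repeated measures ANCOVA. It names no covariate and does not rank these against the growth model. The preliminary analyses will describe arm differences at baseline but give no rule for using them.

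**The concern.** The T0 questionnaires are completed before the first group session, so COPE-P cannot have affected them. A growth model in which the starting level may differ by arm spends information on estimating a T0 difference that the intervention cannot have caused. The treatment effect then becomes a difference in change. Such a contrast gives the T0 score a fixed weight rather than the weight that its correlation with follow-up supports. Two costs follow: a larger variance than the collected data allow, and an estimate that moves with whatever T0 imbalance occurs. Anxiety, stress, depressive symptoms and healthy lifestyle behaviors are all continuous scales, so all four primary outcomes are affected if this model is the one used for them.

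**Working it through.** **Inputs from the documents.** 364 completers and alpha .05 (Sampling). Two intervention and two control groups per time segment (Overview of the design), hence 364/2 = 182 per arm. The effect size in Sampling is 25 or greater with no unit; I take it as .25 SD.

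**Assumed, because the documents give no figure.** Two-sided test; independent women; T0-to-follow-up correlation r0 = .3 to .5; correlation among follow-ups rf = .5 to .6; follow-up SD = 1; T0 SD s = 0.8 or 1.0.

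**1. The plan's own power figure (above 80%).** For one visit without adjustment, power = Φ(.25/√(2/182) − 1.96) = 66.5%, or 77.0% one-sided. An effect of .30 SD gives 81.6%. The mean of three follow-ups, with variance (1 + 2ρ)/3, gives 90%, 83% and 76% at ρ = .3, .5 and .7. The figure depends on a unit and a correlation that are not stated, so it can be neither confirmed nor refuted.

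**2. Mean of T1–T3.** Let v_m = (1 + 2rf)/3, v_0 = s² and c = r0·s. Variance per woman:
- T0 difference free: v_m + v_0 − 2c
- T0 as covariate, or common T0 mean: v_m − c²/v_0

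Power = Φ(.25/√(2v/182) − 1.96).

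| r0 | rf | s | free | adjusted | fall | power free | power adjusted |
|---|---|---|---|---|---|---|---|
| .3 | .5 | 1.0 | 1.067 | .577 | 46% | 64% | 88% |
| .3 | .6 | 1.0 | 1.133 | .643 | 43% | 61% | 84% |
| .4 | .6 | 1.0 | .933 | .573 | 39% | 69% | 88% |
| .5 | .5 | 0.8 | .507 | .417 | 18% | 92% | 96% |
| .5 | .6 | 0.8 | .573 | .483 | 16% | 88% | 93% |

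These rows include the extremes of the whole grid: variance falls 16–46%, and power is 61–92% against 84–96%.

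**3. Single visit.** Free: 1 + s² − 2·r0·s. Adjusted: 1 − r0². At r0 = .3, s = 1: 1.40 against .91, a fall of 35%. At r0 = .5, s = 0.8: .84 against .75, a fall of 11%.

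**4. Higher correlation.** At r0 = .7 with rf from .5 to .8, the mean T1–T3 variance falls from .267 to .177 (34%; rf = .5, s = 1) at most, and from .387 to .377 (about 3%; rf = .8, s = 0.8) at least.

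**5. Linear slope, effect growing linearly to .25 SD at T3.** Generalized least squares with visits coded 0 to 3; true slope .25/3 = .0833. At r0 = .4, rf = .6, s = 1, the SE is .0344 with a free T0 difference and .0303 with a common T0 mean, giving power 68% and 79%. Over the grid of step 2, power is about 60–79% against 75–83%.

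**6. Chance T0 imbalance.** Its SE is √(2/182) = .105 SD. With equally spaced visits, one common correlation r and a free T0 difference, each 1 SD of imbalance shifts the linear-model estimate at T3 by −.63, −.45 and −.27 SD at r = .3, .5 and .7. An imbalance of one SE therefore moves it by .066, .047 and .028 SD, which is 26%, 19% and 11% of a .25 SD effect. With a common T0 mean the shift is 0.

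**The case against.** The strongest reply is that the plan does not commit the primary outcomes to this model. The sentence naming them lists ANCOVA and repeated measures ANCOVA, whose usual covariate would be the baseline score, and assigns growth models to the secondary outcomes. The model equations are absent from the available text, which is not a fault of the plan, and the list of controls is open-ended. This stands in part: the reading rests on prose. But the next paragraph extends the growth model to all continuous outcomes and uses a primary one as its example. An ANCOVA with no covariate or rank does not secure adjustment.

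A reader might also infer more than the documents support:

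- **That COPE-P x Time is the stated test for the continuous scales.** It is named only for the logistic model. For continuous outcomes it is an inference from relating rate of change to arm.
- **That T0 is ignored, or that all its noise is added.** Neither is so. The free form adds v_0 − 2c, not v_0. At a single visit with equal SDs, change has variance 2(1 − r0), which beats unadjusted follow-up once r0 exceeds .5.
- **That the estimate is biased.** Over repeated randomizations it is not.
- **That the slope test loses far more power.** If the .25 SD effect is present from T1 and persists, the case in step 5 gives .39 against .67. Giving the free model the smaller SE raises .39 only to .48, and giving the common-mean model the larger SE lowers .67 only to .56. Precision thus explains about .09 to .11 of the .28 gap. The rest comes from fitting a straight line to a step, and the plan does allow nonlinear time.
- **That entry truncates every primary scale at T0.** The three screening cut-offs are alternatives, so a woman may enter with a low score on one of them. Lifestyle behaviors is not a screening scale.
- **That the same gains apply to the logistic model.** All the formulas here are linear, and no figure is offered for it.

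**Conclusion.** The point holds as one of efficiency and specification. As described, the growth model treats T0 as an outcome with an arm-dependent starting level, and no other part of the plan secures adjustment for the T0 score. Under the stated assumptions, adjustment lowers the variance of the mean T1–T3 contrast by 16–46% and of a single-visit contrast by 11–35%. At a T0-to-follow-up correlation of .7 the fall in the mean T1–T3 variance is about 3–34%. The adjusted form was the more precise in every case computed. Validity of the test over repeated randomizations is not in question.

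The sizes rest on correlations and an SD ratio that the documents do not give, and on reading the effect size as .25 SD. They also treat women as independent although whole session groups are randomized. No intracluster correlation is given, and chance T0 differences may exceed the .105 SD computed here. The Analysis plan should be changed, because the gain costs almost nothing.

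**What to change.** For the four primary scales, state one primary model: T1, T2 and T3 as outcomes, with the T0 score of the same scale as a covariate. Say how the listed ANCOVA and the growth model rank against it.

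The covariate form is preferable for two reasons. Entry selects on the T0 screening scores, and conditioning on T0 avoids having to model the distribution that this selection leaves. It also still adjusts if placement leaves a T0 imbalance, since women join the next available group, already randomized, by gestational age. Keeping T0 as an outcome with one mean shared by both arms is acceptable only if T0 imbalance is purely chance.

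The cost is a few sentences in the Analysis plan and a line of model code. No new data are needed.

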**Hypothesis-driven analyses.** Various bivariate tests (e.g., independent and dependent t-tests, correlations, ANCOVA and repeated measures analyses of covariance) will be used to evaluate differences and longitudinal patterns of change across time and between relevant subgroups (e.g., intervention groups, language groups) for each significant outcome in the preliminary bivariate analyses, (primary outcomes are healthy lifestyle behaviors, anxiety, stress, and depressive symptoms). For secondary outcomes (appropriate weight gain during pregnancy, birth and post-natal outcomes (e.g., mode of delivery, birth weight/length, gestational age, postpartum weight loss and breastfeeding practices) we will fit a series of longitudinal multilevel growth models to the data.

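### The model carrying the COPE-P effect can adjust for therapy begun after assignment, and no decisive analysis is designated for the continuous primary outcomes

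*Combined protocol and SAP*

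**What the plan says.** **Continuous outcomes (Analysis plan).** The growth model starts from a base: "For all continuous outcomes, such as anxiety, the basic model, to which we can add our controls and predictors". The plan then states: "The level 2 submodel will relate the inter-individual differences to intervention group" and to other "time-invariant predictors and controls, such as medication (i.e., antidepressants) and have begun therapy (i.e., in usual care for mental health diagnoses"). This level is to estimate both the initial level and the rate of change. Three further covariates come later: "Subsequent models will contain time-varying covariates (i.e., dose of intervention, weight, exercise) and thus will focus on within-participants effects".

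**Dichotomised outcomes (end of the Analysis plan).** The condition is "Should any of the outcomes need to be dichotomized (i.e., present vs. absent"). The logistic model contains X_k, which "is a set of time-varying covariates measured for each participant", and the plan says that controls and predictors will be added. It declares: "The interaction term COPE-P x Time is the test of the effectiveness of the COPE-P program". The prose lists no member of X_k, and the formula is not shown in the extracted text.

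**Primary outcomes (Hypothesis-driven analyses).** The methods tied to healthy lifestyle behaviours, anxiety, stress and depressive symptoms are "independent and dependent t-tests, correlations, ANCOVA and repeated measures analyses of covariance". Growth models are tied to the secondary outcomes. The next paragraph applies growth models to all continuous outcomes, with anxiety, a primary outcome, as its example.

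**Intention to treat (Missing Data).** All analyses are to follow original random assignment, regardless of adherence.

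**The concern.** Therapy begun during the study is a possible consequence of assignment. If it stands beside arm in the model, the arm coefficient compares women with the same therapy status, which is not the effect of being assigned to COPE-P. The same holds for dose, weight or exercise if any of them serves as X_k.

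The plan also leaves more than one analysis open for the same continuous primary outcomes: tests that name no post-assignment covariate, and a growth model that can include therapy. Neither is designated, so the effectiveness conclusion could depend on which is reported.

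**Working it through.** **When therapy starts.**
- Exclusion criteria: women currently in psychiatric treatment or therapy cannot enter.
- Table 1 and Measures: mental-health referral or prescription after screening is recorded on the demographic form, completed at T0-T3.
- Procedure: placement in an already randomised group follows baseline directly.
- Measures (EPDS): high scores lead to referral. Procedure: the EPDS is repeated at T1, after the sessions.

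Therapy therefore begins after eligibility, and an outcome score can trigger it. A start prompted by the screening score alone would be harmless if equal by arm. Uptake could differ by arm: COPE-P session 3 covers signs of depression and anxiety, and no control pamphlet title names them. The documents do not say whether it does. Nor do they give the timing of antidepressant use.

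**Algebra.** The plan gives no figure on this point to reproduce. Write each woman's slope as g10 + g11·COPE + g12·Therapy + error. With complete balanced data the arm x time estimate equals a regression of individual slopes on arm and therapy. A fitted mixed model on 1,500 simulated women agreed: -0.3268 by both routes unadjusted, -0.2766 by both adjusted. Hence, for T0-T3 change:

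adjusted - unadjusted = -3 × g12 × (uptake in COPE-P - uptake in control).

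The shift is zero if uptake is equal or if therapy has no slope term.

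**Assumed inputs.** Effect -0.25 SD at T1-T3 (Sampling prints 25, read as .25); within-woman correlation .6; 40% of controls above the control median at the trigger visit start therapy; linear time 0-3; no dropout or clustering; 1,500,000 women per setting. Check: an effect of -0.25 at T1-T3 gives a fitted T0-T3 change of 3 × (-0.5 + 0.5 + 1.5) × (-0.25)/5 = -0.225. The simulation gives -.223 to -.226 unadjusted when therapy has no effect.

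**Results.** Unadjusted / adjusted T0-T3 change in SD units, by effect of therapy on later scores:

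| Trigger visit; COPE-P uptake rule | 0 | -0.2 SD | -0.5 SD |
|---|---|---|---|
| T0; same | -.224 / -.224 | -.223 / -.223 | -.225 / -.225 |
| T0; halved | -.224 / -.259 | -.209 / -.261 | -.180 / -.260 |
| T0; doubled | -.226 / -.139 | -.259 / -.137 | -.315 / -.138 |
| T1; same | -.226 / -.232 | -.216 / -.230 | -.203 / -.231 |
| T1; halved | -.224 / -.239 | -.196 / -.239 | -.154 / -.240 |
| T1; doubled | -.224 / -.206 | -.254 / -.207 | -.297 / -.206 |
| T2; same | -.224 / -.219 | -.219 / -.221 | -.206 / -.218 |
| T2; halved | -.225 / -.211 | -.204 / -.211 | -.169 / -.208 |
| T2; doubled | -.223 / -.241 | -.246 / -.242 | -.282 / -.245 |

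The Monte Carlo standard error is about .0014, and the standard error with 364 women is .089-.096. The extreme shifts are -.240 - (-.154) = -.086 and -.138 - (-.315) = +.177. With the same rule in both arms, the largest is -.231 - (-.203) = -.028.

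In the T0, doubled, -0.2 SD setting, the unadjusted change is .259/.096 to .259/.089 = 2.7 to 2.9 standard errors. The adjusted change is .137/.096 to .137/.089 = 1.4 to 1.5.

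**Direction.** A different assumed mechanism has one outcome, a true effect of -0.25, and uptake that may follow underlying symptom course. It gives adjusted effects from -0.16 (uptake 29% control, 14% COPE-P) to -0.36 (29% and 48%), and -0.25 with equal uptake. There lower COPE-P uptake weakens the estimate; in the table's T0 and T1 rows it strengthens it.

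**Logistic model.** Assumed: true COPE-P x Time -0.2 per visit given X_k; X_k log-odds 0.5 per SD; random-intercept SD 1.5. If COPE-P moves X_k towards lower risk by -0.1, 0, 0.1 or 0.2 SD per visit, the odds ratio without X_k is exp(-.146) = 0.86, exp(-.185) = 0.83, exp(-.254) = 0.78 or exp(-.293) = 0.75. With X_k it is 0.81 to 0.83, which is simulation noise around exp(-0.2) = 0.82.

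**The case against.** The control list opens with such as, and controls can be added to the basic model, so a version without therapy is not ruled out. No passage defines when therapy is coded. A flag for care prompted by the screening score would fit the text and do no harm if equal by arm. No therapy-by-time term is written. Fitted as a main effect only (1,500 simulated women, doubled uptake, -0.5 SD therapy effect), therapy left the change at -0.375, as unadjusted; with therapy x time it became -0.198. Of the 27 shifts above, 24 are below .089, and the three larger ones all need doubled uptake.

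These points stand and limit the size. They do not remove the concern. The level-2 text says it will relate differences to arm and these controls, and that it estimates rate of change, so a slope term is a natural reading. The logistic text says controls will be added. Nothing confines therapy to before assignment or makes the control-free version the test. The intention-to-treat statement fixes the arm in which each woman is analysed, not the covariates.

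A reader might infer more than the documents support:
- That no effectiveness test is named at all. One is, for dichotomised outcomes.
- That X_k is dose, weight and exercise. These are the only time-varying covariates named, but for later continuous-outcome models.
- That all the alternative tests are covariate-free. ANCOVA is among them, although no post-assignment covariate is named.
- That bias is established. Uptake by arm is not given.

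**Conclusion.** As written, the plan permits the COPE-P effect to be conditioned on therapy that probably begins mostly after assignment, and on unlisted time-varying covariates if an outcome is dichotomised. It does not say which analysis decides effectiveness for the continuous primary outcomes. That much rests on the text plus a strong inference about timing.

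Size and direction are unknown. Under the growth-model assumptions, material shifts require both that therapy predicts the slope and that uptake differs by arm. The +0.18 SD extreme needs doubled uptake, meaning 80% of above-threshold COPE-P women start therapy, together with a 0.5 SD therapy effect. Confidence is medium. The change is worth making because it is nearly free and protects the main result.

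**What to change.** In the continuous and dichotomised parts of the Analysis plan:

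1. State that the effectiveness test for each primary outcome is COPE-P x Time (or one named group contrast) from the planned growth or logistic model. That model contains only arm, time, arm x time and covariates recorded before assignment, with the planned random effects.
2. Keep therapy or medication begun after assignment, dose, weight, exercise and any other post-assignment X_k out of that model. Medication recorded before assignment may stay.
3. State the timing and coding of the medication and therapy variables.
4. Label models containing post-assignment variables as explanatory, and list X_k there.
5. Report therapy and medication starts by arm and visit.

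The cost is wording and possibly slightly less explained variance. The existing T0-T3 form already records medication and referral or prescription, and the adjusted models remain available.

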## Research Protocol: Healthy Lifestyle Prenatal Care Study

### Aims:

**Specific Aim 1.** Use a RCT to evaluate the short- and more long-term efficacy of the COPE-P program to improve healthy lifestyle behaviors (nutrition and exercise), psychosocial health, and birth and post-natal outcomes in pregnant emotionally distressed minority women as compared to an attention control group.

**Hypotheses 1a (primary outcomes).** Immediately after the COPE-P program, at 4-6 weeks postpartum (3 months post intervention), and at 6 months postpartum (8 months post intervention), COPE-P participants will report higher healthy lifestyle behaviors, and less anxiety, stress and depressive symptoms than will the attention control participants.

**Hypothesis 1b (secondary outcomes).** COPE-P participants will demonstrate more appropriate pregnancy weight gain, better birth outcomes (mode of delivery, birth weight, and gestational age), more appropriate postpartum weight loss, and better breastfeeding outcomes than attention control participants.

**Specific Aim 2.** Examine the role of cognitive beliefs and perceived difficulty in leading a healthy lifestyle in mediating the effects of the COPE-P program on healthy lifestyle behaviors and psychological symptoms in minority pregnant women.

**Hypothesis 2 (theory building exploratory).** The effects of the COPE-P program on participants' healthy lifestyle behaviors and levels of anxiety, stress and depressive symptoms will be mediated by beliefs about their ability to make healthy lifestyles choices and their perceived difficulty in leading a healthy lifestyle.

**Exploratory Aim.** Explore characteristics that may moderate healthy lifestyle behaviors, psychosocial health, and birth and post-natal outcomes (e.g., race/ethnicity, income, age, parity, language, level of education, marital status).

**Research Question:** What is the short and long-term effect of the COPE-P program in high-risk pregnant minority women receiving prenatal care on healthy lifestyle behaviors (nutrition and exercise), psychosocial health (healthy lifestyle beliefs, healthy lifestyle behaviors, anxiety, stress and depression), and birth and post-natal outcomes (gestational age at birth, gender, birth weight, birth length, overall health, mode of delivery, breastfeeding (initiation and duration) versus an attention control group (PregnancyPlus group).

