**Overview of the design.** The study conducted will be a longitudinal randomized block RCT with repeated measures (beginning with screening prior to 19 weeks, group prenatal care in both groups (COPE-P intervention group and PregnancyPlus attention control group) from  $16 \pm 2$  to  $31 \pm 2$  weeks and ending at 6 months postpartum). We will block on race/ethnicity to ensure equal numbers of Hispanic and Black women in the COPE-P and PregnancyPlus groups. There will be a total of 30 groups over the course of the study. There will be 22 English speaking groups and 8 Spanish-speaking groups. We will consent and screen up to 700 women, knowing that approximately half will screen out. In order to achieve our target of 182 Black or Hispanic women who complete the study, and accounting for a 30% attrition rate, we will enroll up to 236 women who screen in at Jacobi Medical Center. Four groups (of at least six women per group) will run in each 18-week time segment (COPE-P intervention is six sessions each three weeks apart). The PregnancyPlus group also will have six group prenatal care sessions each three weeks apart. Each session is 1 hour and 30 minutes to 1 hour and 45 minutes in length. Each group within the 18-week time segment will be randomly assigned (using a sealed envelope technique) as either a COPE-P or PregnancyPlus group. At Jacobi Medical Center in Bronx, NY, for each 18-week time segment, there will be two control groups and two intervention groups. The intervention and attention control groups programming will be delivered in Group Prenatal Care methodology which begins in the second trimester consisting of at least 6 women per group. Participants (18 – 40 years) will be screened prior to their 19th week of pregnancy and recruited into the study from the antepartum clinic.

If a participant does not screen into the study, she will be thanked for her time and interest and paid \$10.00 for her participation in the screening process.

07/30/2021

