At eight months post intervention (**T3** - six months postpartum at the six-month well baby visit), all women will once again be contacted and complete all measures (including weights taken on available pediatric clinic adult scales –same model as prenatal scales). Participants will receive \$50.00 for their participation. Outcome data from charts will be collected by team members blind to group assignment.

If study visits cannot be conducted face-to-face, data will be collected through telehealth methods such as via phone or video call (Zoom or Facetime etc.).

**Sampling.** Women will be recruited from the antenatal clinic if they are: between 18 and 40 years old, in their first trimester with an uncomplicated singleton pregnancy of less than 19 weeks, and self-identify as either Black or Hispanic and can read and speak English or Spanish. A completed sample size of 182 Black and Hispanic women from JMC in the Bronx and 182 Black and Hispanic women from OSU Total Health and Wellness clinics will be required to meet the determined sample size of 364 total (at 4 data collection points for each, resulting in ~1,450 observations). This will have greater than 80% power to detect small to moderate effects (i.e. 25 or greater) between group differences in healthy lifestyle behaviors, psychosocial health, and outcomes testing at alpha = .05 for all proposed models. The sample of 364 will have > .80 to detect a small to medium mediated effect. The sample of 364 will have > .80 to detect a small to medium mediated effect.

**Setting. Jacobi Medical Center** is part of New York City Health + Hospitals (NYC H + H), the largest municipal hospital system in the United States. New York City Health + Hospitals oversees the public health care system in all the five boroughs that comprise New York City. It provides one-fifth of the total number of discharges and more than one-third of the emergency services and hospital-based clinic visits in all of New York City. Jacobi Medical Center is an academic affiliate of the Albert Einstein College of Medicine. Jacobi Medical Center is located in the Bronx. As one of the largest health care delivery facilities in the Bronx and in New York City, Jacobi Medical Center has developed a world- wide reputation of distinction. It is renowned for its primacy in

07/30/2021

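### For the continuous primary outcomes no test of Hypothesis 1a is designated and the shape of time is left to the data; separately, growth models are assigned to birth outcomes recorded once

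*Combined protocol and SAP*

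**What the plan says.** **Hypothesis.** Under Aims, Hypothesis 1a predicts better lifestyle behaviours and fewer symptoms in the COPE-P arm at three times: "Immediately after the COPE-P program, at 4-6 weeks postpartum (3 months post intervention), and at 6 months postpartum (8 months post intervention").

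**Primary outcomes.** Under Hypothesis-driven analyses: "Various bivariate tests (e.g., independent and dependent t-tests, correlations, ANCOVA and repeated measures analyses of covariance) will be used to evaluate differences". The same sentence adds "for each significant outcome in the preliminary bivariate analyses", which can be read as following up only outcomes already significant in a first round of tests. No visit and no single test is named.

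**Continuous model.** The growth model relates arm to each woman's starting level and rate of change. On time: "We will begin with a linear model for time but will investigate nonlinear effects as suggested by the data". No rule is given for leaving the linear form. The random effects described are an intercept and time trend for the woman.

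**Dichotomized outcomes.** Only here does the plan name a test: COPE-P x Time, interpreted as a faster decline in symptoms in the COPE-P arm.

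**Randomisation.** Overview of the design: "Each group within the 18-week time segment will be randomly assigned (using a sealed envelope technique) as either a COPE-P or PregnancyPlus group", and "There will be a total of 30 groups over the course of the study".

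**Power.** Sampling claims "greater than 80% power to detect small to moderate effects (i.e. 25 or greater) between group differences", with "outcomes testing at alpha = .05 for all proposed models".

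**Secondary outcomes.** Longitudinal multilevel growth models are assigned to a list that includes mode of delivery, birth weight/length and gestational age. Table 1 times each of these once, by chart review after delivery.

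**The concern.** A confirmatory hypothesis needs one quantity fixed in advance as its test. Here the analyst could use a difference at any of three visits, a repeated-measures effect, a linear slope, or a curved time effect chosen after looking at the data. Free choice among these raises the false-positive rate for each outcome. Power also depends heavily on the choice: a slope is a weak test of a benefit that is reached by T1 and then held or partly lost.

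If first-round significance decides which primary outcomes are analysed further, the selection is itself made from the data. A model with random effects for the woman only ignores the unit that was randomised.

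The birth-outcome problem is simpler. One record per woman gives no trajectory, so that analysis cannot be run as written.

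**Working it through.** **Inputs from the documents:** 364 completers in total and alpha .05 (Sampling); assessments at T0-T3 (Table 1); 30 groups and a target of 182 completers at the Bronx site (Overview of the design).

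**Assumptions:** equal split, 182 per arm; the 25 in the power statement, which has no unit, read as 0.25 SD; two-sided test; compound symmetry with correlation r; no clustering in steps 1-3; assessments at weeks 0, 15, 29 and 50 (T0 near 16 and T1 at 31 weeks' gestation, delivery taken as 40 weeks, T2 about 5 and T3 26 weeks postpartum).

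**1. The plan's own figure.** 364 x 4 = 1,456, which agrees with the stated approximate 1,450 observations. For a two-sample comparison at one visit, z = 0.25/sqrt(2/182) = 2.38, giving power of 66% (77% one-sided). T0-adjusted ANCOVA at one visit gives 71-92% for r = .3 to .7. So more than 80% is reachable with some contrasts and not others. With contrast and correlation unstated, it can be neither confirmed nor refuted.

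**2. Power by contrast.** Let k = 2/182 = 0.01099, let D be the arm difference in SD units with D = 0 at T0, and let power = P(Z > 1.96 - z). Sustained effect: 0.25 at T1, T2 and T3. Half-fade: 0.25, 0.1875, 0.125. With r = .5:

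- *Slope, T0 difference left free.* Sum((t - 23.5)D)/1357, SE = sqrt(k(1-r)/1357) = 0.00201. Sustained: 5.875/1357 = 0.00433, z = 2.15. Half-fade: 2.219/1357 = 0.00164, z = 0.81.
- *Slope, arms constrained equal at T0.* With c = r/(1+3r) = 0.2, the denominator is Sum(t^2) - c(Sum t)^2 = 3566 - 0.2 x 94^2 = 1798.8, and SE = sqrt(k(1-r)/1798.8) = 0.00175. The numerator is Sum(tD) - c(Sum t)(Sum D). Sustained: 23.5 - 14.1 = 9.4, z = 2.99. Half-fade: 15.4375 - 10.575 = 4.8625, z = 1.55.
- *Average T1-T3 change from T0, unadjusted.* Variance k(4/3)(1-r) = 0.00733, SE 0.0856. z = 0.25/0.0856 = 2.92, or 0.1875/0.0856 = 2.19.
- *T0-adjusted T1-T3 average.* Variance k((1+2r)/3 - r^2) = 0.00458, SE 0.0677. z = 3.69 or 2.77.

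| Contrast | Sustained, r = .3/.5/.7 | Half lost by T3, r = .3/.5/.7 |
|---|---|---|
| Slope, T0 free | 44/58/79% | 10/13/18% |
| Slope, equal at T0 | 86/85/91% | 41/34/34% |
| Average change | 69/83/96% | 46/59/81% |
| T0-adjusted average | 95/96/99% | 77/79/89% |

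Requiring significance at all three visits, the literal reading of Hypothesis 1a, gives 41/55/80% for a sustained effect.

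**3. False positives.** In 400,000 simulated null trials, counting a success if any one of three visit-specific ANCOVAs has p < .05 gives 13-14% per outcome over r = .3 to .7.

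**4. Clustering.** 182/30 = 6.07 completers per prenatal group (same size assumed at the Ohio site). The variance factor is 1 + 5.07 x ICC: 1.10, 1.25 and 1.51 at assumed ICCs of .02, .05 and .10. At r = .5 the T0-adjusted average then has 94/91/85% power (sustained) or 75/70/62% (half-fade).

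**5. Once-recorded outcomes.** No arithmetic is needed. Table 1 gives one post-delivery record for mode of delivery, birth weight, birth length and gestational age. Weight (T0-T3) and breastfeeding (T2, T3) are repeated, so they are not affected.

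**The case against.** **A contrast is named.** A reader might infer that the plan fixes none at all. That goes too far: COPE-P x Time is designated for dichotomized outcomes. It does not settle the continuous case, because it is stated only in that conditional model, tests a faster decline and not a difference at each visit, and is no longer a single coefficient once curved time is admitted.

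**A suitable method is listed.** Repeated-measures analysis of covariance is on the list, and its between-arm effect with T0 as covariate is essentially the T1-T3 average. This stands: the fault is failure to designate, not absence of a usable test.

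**The power gap is partly baseline handling.** A reader might take 58% against 96% as the cost of using a slope. It is not. Constraining the arms to be equal at T0 lifts the slope to 85%, and dropping T0 adjustment lowers the average to 83%. A real loss remains when the effect fades: 34% against 79%, with T0 handled efficiently in both.

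**The false-positive figure assumes unrestricted choice.** Hypothesis 1a joins the visits with *and*. If all three had to be significant, the rate in the benefit direction could not exceed 2.5%. The 13-14% is therefore a ceiling, not a forecast of what the analysts will do.

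**The equations are missing from the available text.** True, so time coding is not criticised. An equation would show the terms in the model, but the prose would still not say which term tests the hypothesis.

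**Conclusion.** The point holds in two parts. First, for the continuous primary outcomes the plan designates no test of Hypothesis 1a, can be read as carrying forward only outcomes significant in preliminary tests, lets the data choose the shape of time, and describes no random effect for the randomised prenatal group. Second, growth models are assigned to four birth measures recorded once, which is a small but definite mismatch.

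Both parts rest on the text. The sizes are illustrative and depend on the assumptions listed in the working: at r = .5, power of 58-96% for a sustained effect of 0.25 SD and 13-79% for a half-fade, and at most about 13-14% false positives per outcome if any visit may count.

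The documents do not support two stronger conclusions: that the stated power is wrong, since it cannot be checked either way, or that the T1-T3 average is the only right contrast. This should be corrected before outcomes are compared by arm.

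**What to change.** - Analyse every primary outcome, whatever the preliminary tests show.
- Pre-specify one mixed model for each: categorical visit (T1-T3), arm, arm x visit, the T0 score as covariate, and random effects for woman and for randomised prenatal group. Women given the content 1:1 stay in their assigned group.
- Name one contrast per outcome before unblinding. The T1-T3 average is a reasonable option. Report the T1, T2 and T3 differences with confidence intervals, and do not claim a difference at each visit from the average alone.
- Keep growth curves as descriptive. If an outcome is dichotomized, test the same named contrast in the logistic model.
- For birth weight, birth length and gestational age use linear regression, and for mode of delivery logistic or multinomial regression, each allowing for prenatal group.
- State the unit of the effect size and restate power for the named contrast with clustering.

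The cost is SAP wording only; visits and measures do not change. The average has a downside. If the benefit grows steadily to 0.25 SD at T3 (D = 0.25t/50), it has less power than the T0-free slope at moderate or high correlation: 64% against 70% at r = .5, and 77% against 89% at r = .7. At r = .3 it has slightly more (61% against 56%). One test per outcome still leaves four primary tests at .05, which is a separate matter.
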